9.2.1 LVEF on Echocardiography at 6 Months and 1 Year

Baseline, 6-month and 12-month echocardiograms will be anonymised and submitted to an independent echocardiography core laboratory (at Guy's and St Thomas' Hospital, London, UK), which will determine LVEF using a Simpson's biplane method for evaluation of the major secondary outcome. Anonymised scans were read by core laboratory readers who were blinded to treatment assignment and also the timing of each echo in relation to randomisation.

Where echocardiograms were not performed at precise follow-up intervals (for example, due to restrictions related to the COVID-19 pandemic), echocardiograms recorded between 4 months to 9 months post-randomisation will be considered as the planned 6-month measure, those recorded from 9 months to 24 months post-randomisation will be considered as the planned 1-year measure and the mean (SD) delay from randomisation to each echocardiogram reported. For patients who die a

value of 0% will be imputed for the primary analysis with a secondary sensitivity analysis excluding these patients.

The mean % LVEF at 6 months and 1 year in each treatment group, together with the absolute difference between these measures (and its associated p-value and 95% confidence interval), will be estimated using a linear mixed effects model for repeated measures as described by Frost, Kenward and Fox.¹

This linear mixed model is an extension of a simpler model suggested by White and Thompson as an alternative to the standard analysis of covariance (ANCOVA) model commonly used for the analysis of clinical trials with only a single follow-up measure of the outcome plus a baseline measure. Key features of the White and Thompson model are that the baseline measure is included in the model as an additional outcome that is allowed to be correlated with the follow-up measure, and whose mean is assumed to be the same in both arms of the trial. In the absence of missing data, the White and Thompson model gives identical effect estimates and virtually identical standard errors to the more standard ANCOVA model. Where there are missing data, the White and Thompson approach has the advantage that patients for whom the follow-up measure is present but the baseline measure is missing can be included in the analysis. It also extends naturally to the model proposed by Frost, Kenward and Fox for the situation where there are multiple follow-up measures.

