4.1. Sample size

In REVIVED-BCIS2 all patients underwent viability imaging prior to randomisation; at least four viable segments which could be revascularised by PCI were required for inclusion. Of the 700 patients enrolled, viability was assessed with CMR in 491 and DSE in 187. Primary outcome data are available for 99.1% of patients. Serial echocardiographic data are available for a subset of these patients.

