6.2. Secondary outcomes

While several secondary clinical outcomes were specified in the main trial protocol, for the Viability Study SAP, these will be restricted to all-cause death, cardiovascular death and heart failure hospitalisation, each analysed in the same manner as the primary composite outcome. Improvement of left ventricular function at six months is the key secondary outcome and will be defined in a binary manner, as an improvement in LV ejection fraction greater than the median change in LVEF at six months.

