6.4. Missing data

Missing viability data will not be imputed – participants whose viability studies are either not available or are not suitable for analysis will be excluded. For patients who have survived more than 6 months, missing values of ejection fraction will be imputed using multiple imputation by chained equations

with randomised treatment, age, sex, and baseline, 6-month and 12-month ejection fraction included in the imputation model. Twenty imputed datasets will be generated and effect estimates and corresponding confidence intervals calculated using Rubin's rules. Other rules for handling missing data will follow the main trial SAP. A sensitivity analysis will be performed limited to patients who have echocardiography data available at baseline and 6-months.

7. Statistical analysis

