7.3. Improvement in left ventricular function and event-free survival

A Cox proportional hazards model will be used to assess the relationship between the improvement in left ventricular function (as a binary effect) on the primary outcome. Multivariable Cox analyses will be used to adjust the analysis for the list of baseline factors in section 7.1. The interaction between improvement in left ventricular function and treatment assignment on even-free survival will then be assessed using a Cox proportional hazards model containing the following co-variates: improvement in left ventricular ejection fraction (treated as a binary effect), randomly assigned treatment, and their interaction, plus the aforementioned list of baseline risk factors. Kaplan-Meier plots will be presented stratified by improvement in left ventricular function and treatment assignment presented. These analyses will be limited to patients who did not experience a primary outcome event in the first six months after randomisation. In secondary analyses, change in left ventricular ejection fraction will be treated as a linear effect.

8. Appendix 1: Cardiac Magnetic Resonance Secondary Analyses

This appendix describes subsequent planned analyses based on CMR data alone.

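### Viability Study SAP 6.4: the ejection fraction imputation model omits viability, viability by treatment and the clinical outcome, which biases the imputed-EF analyses in 7.2 and 7.3 towards the null

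*Protocol*

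**What the plan says.** Section 6.4 of the Viability Study SAP covers patients who survive beyond six months. Their missing EF values are imputed by chained equations, "with randomised treatment, age, sex, and baseline, 6-month and 12-month ejection fraction included in the imputation model". It continues: "Twenty imputed datasets will be generated and effect estimates and corresponding confidence intervals calculated using Rubin's rules". Viability is treated differently: "Missing viability data will not be imputed", and patients without a usable viability study are excluded. A sensitivity analysis uses only patients with baseline and 6-month echocardiograms. On the amount missing, section 4.1 says only: "Serial echocardiographic data are available for a subset of these patients".

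The imputed EF is used as follows.

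- Section 6.2 defines recovery, the key secondary outcome, as "an improvement in LV ejection fraction greater than the median change in LVEF at six months".
- Section 7.2 relates recovery to the number of viable segments in Cox models. It then tests viability by treatment, adjusting for the eight factors listed in 7.1. It also plans a repeated-measures mixed model for EF change with terms for time, viability and their interaction.
- Section 7.3 makes recovery the exposure and death or heart failure hospitalisation the outcome, with a recovery by treatment test. It adds: "These analyses will be limited to patients who did not experience a primary outcome event in the first six months after randomisation".

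Section 7.1 relates viability, and viability by treatment, directly to the primary outcome. EF enters there only as a baseline adjustment factor.

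**The concern.** An imputation model should contain every variable whose association with the imputed quantity is later tested. If it does not, the imputed values are drawn as though the association were absent, given the variables that were included. Pooling true values with such draws weakens the association. Rubin's rules account for uncertainty under the imputation model; they do not restore a relationship that the model left out.

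This study's primary objective (section 3.1.1) has two halves: whether viability predicts the effect of PCI on clinical outcomes, and whether it predicts the effect on functional recovery. The second half rests on the 7.2 interaction test. The likely error is a finding that viability, or recovery, does not matter when in fact it does.

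**Working it through.** **1. Variables imputed with, against variables analysed**

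| Variable | In 6.4 imputation model | Used in 7.2 Cox | Used in 7.3 |
|---|---|---|---|
| Treatment, age, sex, baseline EF | yes | yes | yes |
| 12-month EF | yes | as 12-month recovery | no |
| Number of viable segments | no | tested | no |
| Viability by treatment | no | tested | no |
| Modality, previous heart failure hospitalisation, diabetes, extent of coronary disease, chronic renal failure | no | adjusted for | adjusted for |
| Primary-outcome event and time | no | no | is the outcome |

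Three of the eight 7.1 factors (age, sex, EF) are in the imputation model and five are not. Viability is fully observed in the analysis set because patients without it are excluded, so nothing prevents its use.

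**2. A benchmark by hand**

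Let f be the share of 6-month EF missing completely at random, and suppose 12-month EF is missing in the same patients. Given treatment, age, sex and baseline EF, the imputed values then have zero slope on viability, and the observed ones have the true slope b. In a linear model the combined slope is

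(1 - f) x b + f x 0 = (1 - f) x b.

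For f = 0.1, 0.2 and 0.4 the ratio to the truth is 0.90, 0.80 and 0.60. The same holds for viability by treatment. An observed 12-month EF carries part of the viability signal and raises the ratio.

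**3. Simulation**

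The documents state neither a missing fraction nor a bias, so there is no planned figure to reproduce. The following were assumed:

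- 6-month EF missing completely at random in 10, 20 or 40%; baseline EF complete.
- Three patterns for 12-month EF: missing together with 6-month EF; seen in half of those lacking 6-month EF; missing independently in 20%.
- 0.4 EF points per viable segment, plus 0.6 per segment under PCI; log hazard ratio of -0.7 for recovery.
- Logistic regression standing in for the 7.2 recovery model; Cox regression for 7.3 and 7.1.
- 3000 patients, 3 replicates and 2 imputations per cell. The Monte Carlo noise is several points.

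Ratio of the estimate under the planned imputation to the full-data estimate (range over the three patterns):

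| Estimate | 10% missing | 20% | 40% |
|---|---|---|---|
| 7.2 viability and recovery (log odds) | 0.87-0.99 | 0.79-0.93 | 0.59-0.81 |
| 7.2 viability by treatment (log odds) | 0.93-0.95 | 0.83-0.98 | 0.43-0.90 |
| 7.3 recovery and primary outcome (log HR) | 0.90-0.93 | 0.81-0.88 | 0.57-0.69 |
| 7.1 viability and primary outcome | 1.00 | 1.00 | 1.00 |

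When both follow-up EFs are missing together, the viability ratios are 0.87, 0.79 and 0.59, close to the hand benchmark. The interaction ratio of 0.43 at 40% lies well below the benchmark of 0.60 and is probably low through noise.

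On the hazard ratio scale, a full-data value of exp(-0.7) = 0.50 becomes:

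- 20% missing: exp(-0.7 x 0.88) = 0.54 to exp(-0.7 x 0.81) = 0.57.
- 40% missing: exp(-0.7 x 0.69) = 0.62 to exp(-0.7 x 0.57) = 0.67.

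**4. After adding viability, viability by treatment, event indicator and cumulative hazard**

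- 7.2 viability: 0.95-1.09. 7.2 interaction: 0.96-1.11, across all missing fractions.
- 7.3 log HR: 0.94-0.96 at 10%, 0.91-0.99 at 20%, 0.76-0.89 at 40%. This is better, but not fully restored.

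Complete-case ratios for 7.2 and 7.3 ran from 0.93 to 1.19 without systematic attenuation. Under these assumptions the planned main analysis is more biased than its own sensitivity analysis.

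**The case against.** The strongest reply is that the damage is contained, and much of that stands.

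- A reader might infer that every association in the viability study is biased. The documents do not support this. Section 7.1, which covers the primary clinical outcome and the first half of the primary objective, does not use 6-month EF; at most its baseline EF adjustment term could be imputed.
- The 7.2 mixed model takes incomplete EF directly under missing at random, so its viability estimate escapes this bias. It lists no viability by treatment term, however, so it does not replace the interaction test. It also offers nothing for 7.3.
- A reader might also infer that imputed EFs are drawn as if wholly unrelated to viability. That is too strong, because 12-month EF is in the model and, where observed, carries part of the signal.
- The complete-case analysis could reveal a material divergence. It is only a sensitivity analysis, though, and its lack of attenuation was shown only for data missing completely at random.
- The missing share is unknown. If it is small and 12-month EF is mostly present, the loss is a few per cent.

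For 7.3 there is a separate matter that runs the other way. The main SAP (9.2.1) allows that "echocardiograms recorded between 4 months to 9 months post-randomisation will be considered as the planned 6-month measure" where scans were off schedule, while 7.3 excludes only patients with events in the first six months. If that window applies here, a heart failure admission at month 7 could lower an EF measured at month 8 and exaggerate the association. The Viability Study SAP does not restate the window and this effect was not quantified. The dilution from imputation is therefore established for 7.3, but the net direction of all biases there is not.

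**Conclusion.** The point holds for the analyses that use imputed EF: the Cox recovery models in 7.2, including viability by treatment, and the recovery-to-outcome models in 7.3. The imputation model in 6.4 is incompatible with these analyses and pulls their estimates towards the null. Section 7.1 and the viability effect in the 7.2 mixed model are outside it.

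The direction follows from the listed variables. The size is conditional on the share of EF missing, on how often 12-month EF is missing too, on missingness completely at random and on the assumed effects. At 10% missing the loss is about 1 to 13% of the coefficient, depending on the analysis. At 20% it is 2 to 21%. At 40% it is 10 to 57%, where the upper end is probably inflated by noise and about 40% is the better guide from the hand calculation.

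**What to change.** In Viability Study SAP 6.4, add to the imputation model:

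- the number of viable segments and testing modality;
- viability by treatment, or impute separately within each arm;
- the remaining 7.1 factors: previous heart failure hospitalisation, diabetes, extent of coronary disease and chronic renal failure;
- the primary-outcome event indicator and the Nelson-Aalen cumulative hazard.

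Impute EF as a continuous variable and derive recovery afterwards. For 7.3, preferably use an imputation compatible with the Cox model, since simply adding the event terms removes only part of the bias. Report the share of EF missing at each visit.

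Separately, state which time window defines the 6-month EF. If it is the main SAP's 4 to 9 months, start the 7.3 risk time at the echocardiogram date or at the end of the window.

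The cost of the imputation change is a few sentences and a longer command; no new data are needed. The compatible imputation takes more programming. Moving the start of risk time loses some early events, and how many cannot be worked out from the documents.

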7.2. Viability and improvement in left ventricular ejection fraction

A Cox proportional hazards model will be used to assess the relationship between the number of viable myocardial segments (treated as a linear effect) and recovery of left ventricular function at six and twelve months. Multivariable Cox analyses will be used to adjust the analysis for the list of baseline factors in section 7.1. The interaction between viability and treatment assignment on improvement in left ventricular function will then be assessed using a Cox proportional hazards model containing the following co-variates: viability (treated as a linear effect), randomly assigned treatment, and their interaction, plus the aforementioned list of baseline risk factors. In secondary analyses, the extent of viability will be divided into tertiles and Kaplan-Meier curves stratified by both viability tertile and treatment assignment presented. A sensitivity analysis will be performed where viability is defined irrespective of resting dysfunction (including segments with normal function at rest and with $\leq 25\%$ scar on CMR or contractile reserve on DSE).

The relationship between the number of viable segments and recovery of left ventricular function will also be assessed using the change in ejection fraction at 6 and 12 months with a linear mixed effects model for repeated measures adjusting for the variables specified in section 7.1⁷. This model accounts for the baseline ejection fraction, while also incorporating both follow-up measurements, and enables the inclusion of participants with missing measurements. The mean change in ejection fraction at each timepoint along with the association between viability and these means will be estimated. The model includes a variable for time, viability, and an interaction between time and viability, and assumes no effect of treatment at baseline. An unstructured variance-covariance matrix will be used to allow for correlations between repeated measures of ejection fraction. The model will be fitted using restricted maximum likelihood and assumes that missing ejection fraction values are missing-at-random.

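### The Viability SAP imputes missing ejection fraction without viability or clinical events in the model, which pulls the recovery analyses in 7.2 and 7.3 towards no effect

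*Protocol*

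**What the plan says.** The Viability Study SAP settles the imputation in some detail. For patients who survive more than six months, "missing values of ejection fraction will be imputed using multiple imputation by chained equations". The plan then names the variables for those equations; the imputation is to run "with randomised treatment, age, sex, and baseline, 6-month and 12-month ejection fraction included in the imputation model". Pooling is also fixed: "Twenty imputed datasets will be generated and effect estimates and corresponding confidence intervals calculated using Rubin's rules". Remaining missing-data rules defer to the main SAP, whose section 6.5.2 says only that suitable methods will be considered and names no imputation variables.

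The imputed EF is used in two places:

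- **Section 7.2.** EF recovery is the outcome. It is defined in 6.2 "as an improvement in LV ejection fraction greater than the median change in LVEF at six months". The model for effect modification contains "viability (treated as a linear effect), randomly assigned treatment, and their interaction", plus baseline risk factors.
- **Section 7.3.** EF improvement becomes the exposure for the primary outcome. The model contains "improvement in left ventricular ejection fraction (treated as a binary effect), randomly assigned treatment, and their interaction".

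Section 4.1 says that "viability was assessed with CMR in 491 and DSE in 187", and that "Serial echocardiographic data are available for a subset of these patients". It does not say how large that subset is.

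Two other analyses bear on the point. Section 6.4 plans a sensitivity analysis in patients with both a baseline and a six-month echocardiogram. Section 7.2 also plans a likelihood-based mixed model of EF change that needs no imputation.

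**The concern.** Multiple imputation preserves an association only if the imputation model allows for it. Here missing EFs are drawn as if, given treatment, age, sex and the other EFs, they had no relation to viability or to later events. Those are the relations that 7.2 and 7.3 set out to measure. Mixing such draws with observed values dilutes any true association.

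Whether viability predicts the effect of PCI on functional recovery is one half of the study's primary objective (3.1.1), and six-month improvement is its key secondary outcome (6.2). The dilution favours the conclusion that viability does not matter, so a null interaction in 7.2 could not be told apart from a product of the imputation.

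**Working it through.** The plan gives no figure for this, so there is nothing to reproduce first.

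**1. Listed variables against what the analyses need**

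| Term | In the 6.4 list | Used with imputed EF |
|---|---|---|
| Randomised treatment, age, sex, three EFs | yes | 7.2, 7.3 |
| Number of viable segments | no | 7.2, tested term |
| Viability by treatment | no | 7.2, tested term |
| Testing modality, other 7.1 risk factors | no | 7.2, 7.3, adjustment |
| Primary event and its time | no | 7.3, outcome |

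**2. Direction and rough size.** Let m be the share of patients with imputed six-month EF. If their 12-month EF is also missing, the imputed change carries no viability signal beyond the listed variables. On a linear scale the pooled slope is then about (1 − m) × β + m × 0 = (1 − m)β, that is 90, 80, 70 and 60% of the truth at m = 10, 20, 30 and 40%. An observed 12-month EF returns part of the signal.

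**3. Simulation.** Assumptions, none of them from the documents: 600 patients; baseline EF mean 28, SD 8; viable segments mean 6, SD 3; each SD of viability adds 2.5 EF points on average, with a between-arm difference in slope of 2.0; patient-level and visit-level SDs of 5 each; six-month EF missing completely at random; 5% of baseline EFs also missing (when 12-month EF is missing with six-month EF, only among patients whose six-month EF is present). There were 20 imputations and 150 simulated trials per setting. Recovery was analysed by logistic regression, because it is a yes/no status at a fixed visit, and events as a log rate ratio. Log-scale estimates under the 6.4 model, as % of the full-data value:

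| Missing six-month EF | 10% | 20% | 30% | 40% |
|---|---|---|---|---|
| *12-month EF missing with it* | | | | |
| Viability → recovery | 87 | 76 | 67 | 56 |
| Viability × treatment → recovery | 86 | 75 | 61 | 50 |
| EF improvement → events | 88 | 80 | 71 | 63 |
| *12-month EF missing independently* | | | | |
| Viability → recovery | 91 | 86 | 77 | 69 |
| Viability × treatment → recovery | 90 | 85 | 78 | 63 |
| EF improvement → events | 90 | 82 | 77 | 68 |

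Adding viability, viability by treatment, the event indicator and the Nelson-Aalen cumulative hazard to the imputation model brings every cell to 97–103%.

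**4. A second simulation under other assumptions** (640 patients, missing at random). The interaction keeps 89/76/66/55% when the 12-month EF is also missing, and 92/79/73/63% when half of those patients have it. Adding viability and its interaction restores 99–102%. For 7.3, a true hazard ratio of 0.50 gives:

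| Missing EF | 6.4 model: HR, ln(HR)/ln(0.50) | With event terms: HR, ln(HR)/ln(0.50) |
|---|---|---|
| 10% | 0.54, 89% | 0.52, 94% |
| 20% | 0.57, 81% | 0.53, 92% |
| 30% | 0.62, 69% | 0.54, 89% |

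Here the event terms remove much of the 7.3 shrinkage but not all of it.

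**5. Where the bias does not reach.** In 7.1 viability is not imputed and EF is one adjustment covariate, so at most confounding by EF is adjusted for less fully. The mixed model in 7.2 contains viability and its interaction with time and handles missing EF by likelihood, so that association is not shrunk. Its listed terms do not include viability by treatment.

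**The case against.** Three counter-arguments have weight.

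- **An unaffected analysis is already planned.** The mixed model estimates the viability–recovery association without imputed values. This stands for that association. It does not cover effect modification by treatment, because no such term is listed, and 7.3 has no likelihood-based counterpart.
- **The observed-echo analysis would expose the problem.** If missingness depends only on variables in the analysis model, that analysis is close to unbiased for 7.2, and the shrinkage would show as a gap between two planned results. This is fair, but it makes the sensitivity analysis the more trustworthy of the two, and the plan treats the imputed result as the main one.
- **The sizes depend on assumptions.** The missing share, effect sizes and EF correlations are not in the documents. Recovery was simulated with a logistic model where 7.2 plans a Cox model. The simulation in step 3 did not apply the restriction in 7.3 to patients without a primary event in the first six months. In the second simulation about half of the 7.3 shrinkage at 10% missing, and about a third at 30%, remained after the fix. All of this stands, so the percentages are illustrations.

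One could also say that 6.4 names what is included without excluding other variables. Taken as written, however, the list is the specification, and no other section adds to it.

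A reader might infer that the whole viability study is biased towards the null. The documents do not support this: the clinical-outcome half of the objective rests on 7.1, where the tested exposure is not imputed. Nor does the point touch the main trial's primary analysis, which uses no imputed EF.

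**Conclusion.** The imputation model in 6.4 is too narrow for two of the analyses it feeds. The binary recovery analyses in 7.2, above all the viability-by-treatment test, and the improvement-versus-events analysis in 7.3 will be pulled towards no effect. The direction follows from the omission. The size grows roughly with the share of missing EF, which is not stated: for 10–40% missing, about 50–92% of the log-scale interaction is kept across the two simulations, under assumed effect sizes and a logistic stand-in for the planned model. If few echocardiograms are missing, the loss is small.

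This should be fixed. It is not a threat to the trial as a whole, since it concerns a secondary viability study, part of 7.2 is protected by the mixed model, and an observed-data check is planned.

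**What to change.** Rewrite the variable list in section 6.4 of the Viability SAP:

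- Impute EF separately by arm, or include viability by treatment.
- Add the number of viable segments, the testing modality and the remaining 7.1 covariates.
- Add the primary-event indicator and the Nelson-Aalen cumulative hazard. Imputation compatible with the analysis model is an alternative.
- Derive the binary recovery variable after imputation, from the imputed EFs.
- Keep the 20 imputations and the observed-echo sensitivity analysis, and report the number of imputed EFs by arm so that readers can judge their influence.

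The cost is a sentence or two of SAP wording and a longer variable list in the imputation code. No new data are needed.
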